17.0 Pathology Considerations/Tissue Biospecimens – Not applicable

18.0 Records and Data Collection Procedures

18.1 Submission Timetable

NOTE: Access the RAVE system through the iMedidata portal at
 [REDACTED] All data must be entered by Remote Date Entry (RDE) and completed by qualified and authorized personnel. All data on the CRF must reflect the corresponding source document. Please refer to the ACCRU website for instructions
 [REDACTED]

Initial Material(s)

| CRF | Active-Monitoring Phase (Compliance with Test Schedule Section 4.0) |
|--|--|
| Institutional Contacts | |
| On Study | ≤2 weeks after registration |
| Laboratory Tests and Results: Baseline | |
| Patient Status: Baseline | |
| Concomitant Medications | |
| Off Treatment | Submit ≤1 week after registration if withdrawal/refusal occurs prior to beginning protocol therapy |

Test Schedule Material(s)

| CRF | Active Monitoring Phase (Compliance with Test Schedule Section 4.0) | |
|--|--|---------------------|
| | At each monthly evaluation during treatment | At end of treatment |
| Treatment (Intervention) | X | X |
| Treatment (Intervention): Dose Omissions | X | X |
| Recurrent Thromboembolism | X | X |
| Adverse Events: Solicited | X | X |
| Adverse Events: Other | X | X |
| Non-CTCAE Bleeding Grading | X | X |
| Concomitant Medications | X | X |
| Patient Status: Treatment | X | |
| Off Treatment | | X |
| ADR/AER | At each occurrence (see Section 10.0) | |
| Deviation | At each occurrence (see Section 10.0) | |

19.0 Budget

- 19.1 Each site should review the test schedule (Section 4.0), taking into account local and regional coverage policies, to determine which items are standard of care and which are research at their site. Refer to the payment synopsis for funding provided per accrual for covering study costs, as well as any additional invoiceables that may be allowed.
- 19.2 Tests to be research funded: none.
- 19.3 Other budget concerns: The study drug, apixaban (2.5 mg or 5 mg), will be supplied free of charge by Bristol Myers-Squibb.

Appendix II
Strong CYP3A4 Inhibitors/Inducers

| | Strong CYP3A4 Inhibitors | Strong CYP3A4 Inducers |
|----------------------------|---|--|
| Antibiotics | Clarithromycin Telithromycin | Rifampin Rifabutin |
| Antidepressants | Nefazodone | |
| Antifungals | Itraconazole Ketoconazole | |
| Protease Inhibitors | Posaconazole Voriconazole Atazanavir Boceprevir Darunavir Delavirdine Indinavir Lopinavir Nelfinavir Ritonavir Saquinavir Tipranavir | |
| Anticonvulsants | | Carbamazepine Phenobarbital Phenytoin Fosphenytoin Primidone |
| Other | | St John's wort |

Appendix III

Khorana Score

The Khorana score is a simple validated risk model for predicting rates of VTE in cancer outpatients receiving chemotherapy, using baseline clinical and laboratory variables. This risk model incorporates five predictive variables for VTE including: site of cancer (2 points for very high-risk site; 1 point for high risk site), platelet count $\geq 350 \times 10^9/L$ (1 point), hemoglobin $< 10 \text{ g/dL}$ and/or use of erythropoiesis stimulating agents (1 point), leukocyte count $> 11 \times 10^9/L$ (1 point), and body mass index $\geq 35 \text{ kg/m}^2$ (1 point) (1). Based on their score, patients are then divided into low (0 points), intermediate (1 - 2 points) or high risk (≥ 3 points). Rates of venous thromboembolism over the ensuing 2.5 months were 0.3 - 0.8% in low-risk, 1.8 - 2% in intermediate-risk, and 6.7-7.1% in high-risk groups.

Very high risk sites include stomach and pancreas cancers. High risk cancer sites include lung, lymphoma, gynecologic, bladder, and testicular cancers.

Risk assessment can be promptly carried out using an online calculator:

[REDACTED]

Appendix IV
Non CTCAE Bleeding Grading Scale
Based on The International Society on Thrombosis and Haemostasis (ISTH) guidelines

| Grade | Symptom |
|--------------|--|
| 1 | 
Minor bleed
 
Minor bleeding is defined as overt bleeding that did not meet criteria for major bleeding or clinically relevant non-major bleeding.
 |
| 2 | 
Non-Major bleed
 
Clinically relevant non-major bleeding is defined as overt bleeding not meeting the criteria for major bleeding but associated with medical intervention, an unscheduled contact with a member of the health care team, or temporary cessation of study treatment.
 |
| 3 | 
Major bleed
 
Major bleeding is defined as overt bleeding plus a hemoglobin decrease of ≥ 2 g/dL or transfusion of ≥ 2 units of packed red blood cells, or intracranial, intraspinal, intraocular, retroperitoneal, pericardial or fatal bleeding.
 |

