2.0 Goals

2.1 Primary Safety Endpoint

2.11 The primary safety endpoint will include the combined endpoint: any episode of major bleeding including fatal bleeding or clinically relevant non major bleeding. In particular, we will consider the proportion of patients who experience at least one such bleeding event within 12 months of beginning treatment. The following criteria will be used to confirm and categorize a bleeding episode:

- Major bleeding is defined as overt bleeding plus a hemoglobin decrease of ≥ 2 g/dL or transfusion of ≥ 2 units of packed red blood cells, or intracranial, intraspinal/epidural, intraocular, retroperitoneal, pericardial, intra-articular, intramuscular with compartment syndrome or fatal bleeding. Intracranial hemorrhage includes intracerebral (hemorrhagic stroke), subarachnoid, and subdural bleeds (21).
- Clinically relevant non-major bleeding is defined as overt bleeding not meeting the criteria for major bleeding but associated with medical intervention, an unscheduled contact with a member of the health care team, or temporary cessation of study treatment.
- Minor bleeding is defined as overt bleeding that did not meet criteria for major bleeding or clinically relevant non-major bleeding.

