4.0 Test Schedule

| Tests and procedures | ≤ 30 days prior to registration (baseline) | Every 30 days after the start of treatment (± 1 week) ³ | End of treatment |
|--|---|---|------------------|
| History and exam (including height and weight) | X | | |
| ECOG PS | X | X | |
| Adverse event assessment ³ | X | X | X |
| Hematology: 
 • CBC | X ¹ | | |
| Chemistry: 
 • SGOT (AST) or ALT • Creatinine | X ¹ | | |
| Selected concomitant meds ³ (see CRF for this form) | X | X | X |
| Pregnancy test ² | X | | |
| Patient education regarding signs and symptoms of thrombosis (Appendix VI) | X ⁵ | | |
| Patient Contact (including bleeding assessment, see App. IV and V) ³ | X | X | X |
| Patient compliance documentation ⁴ | | X | X |

1

1. ≤ 30 days prior to registration.
2. For women of childbearing potential only. Negative serum or urine pregnancy test done ≤ 7 days prior to registration.
3. If it is not feasible for the patient to return to the enrolling center for the monthly reassessment, a detailed history will be obtained by phone using a structured interview (see appendix V).
4. Use the questions in Appendix VII to obtain this information, and document the information on the appropriate case report form.
5. Prior to 1st study drug administration: Appendix VI given to patient and patient educated on signs/symptoms of potential thrombosis to monitor and report to study staff.

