8.0 Dosage Modification Based on Adverse Events

8.1 Apixaban is cleared through several mechanisms including renal clearance, hepatic metabolism, and fecal excretion. Severe thrombocytopenia, liver and renal failure may increase bleeding risk. Patients with calculated creatinine clearance ≤ 30 ml/min (using the Cockcroft-Gault formula) must hold treatment until renal function improves to creatinine clearance >30 ml/min. They may get alternative anticoagulation treatment during this time period until renal function improves per the attending physician judgment.

For patients receiving either a strong CYP3A4 inducer or a strong CYP3A4 inhibitor (Appendix II), the medication should be discontinued or an alternative agent within the specific class of drug should be sought in order to participate in this study. If no good alternative agent within that class can be identified and the drug is required, the ACCRU Data Manager should be notified and the subject removed from the trial and go to observation.

For thrombocytopenia ($> 50,000/\text{microliter}$), no dose adjustment is necessary. For thrombocytopenia ($< 50,000/\text{microliter}$), apixaban will be held until platelet count recovers. Once the platelet count improves ($\geq 50,000/\text{microliter}$), the apixaban dose should be restarted.

If patients meet criteria for a major bleed, they will have met a major safety endpoint and will be removed from the study. The patient will then be managed, off-study, as appropriate per the clinical situation and current guidelines.

If patients meet criteria for a recurrent venous thromboembolic event, they will have met a major secondary endpoint and will be removed from the study. The patient will then be managed, off-study, as appropriate per the clinical situation and current guidelines.

If the patient suffers a non-major clinically relevant bleeding event, they will have met a major safety endpoint. Medical management will be provided in accordance with the location and severity of the bleeding event. This may include temporary cessation of study medication. Once the bleeding event has been appropriately managed, they can restart study medication, if considered clinically appropriate by the attending physician, and can be followed appropriately per protocol. They do not need to be removed from the study for this event.

8.2 Patients requiring any invasive procedure requiring temporary anticoagulant cessation will be managed as follows:

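### The Grade 3 bleed in Appendix IV omits two of the eight site-or-outcome categories that Section 2.11 counts as major bleeding

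*Combined protocol and SAP*

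**What the plan says.** Section 2.11 introduces its definitions with "The following criteria will be used to confirm and categorize a bleeding episode". A bleed is major on either of two grounds. The first is "overt bleeding plus a hemoglobin decrease of ≥ 2 g/dL or transfusion of ≥ 2 units of packed red blood cells". The second is a list of sites or outcomes that qualify whatever the hemoglobin fall or transfusion: "intracranial, intraspinal/epidural, intraocular, retroperitoneal, pericardial, intra-articular, intramuscular with compartment syndrome or fatal bleeding".

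Appendix IV gives a three-grade scale: 1 minor, 2 clinically relevant non-major, 3 major. Its hemoglobin and transfusion criteria, and its wording for Grades 1 and 2, match Section 2.11. Its list for Grade 3 is shorter: "intracranial, intraspinal, intraocular, retroperitoneal, pericardial or fatal bleeding".

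Sites are directed to the appendix. The test schedule in Section 4.0 has a row "Patient Contact (including bleeding assessment, see App. IV and V", marked at baseline, every 30 days and at end of treatment. Section 18.1 lists a form called "Non-CTCAE Bleeding Grading", due at each monthly evaluation and at end of treatment. No section says which definition prevails.

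**The concern.** The trial exists to compare bleeding between two doses, yet the scale cited for routine bleeding assessment is narrower than the endpoint definition. The same bleed can be major in one place and non-major in the other.

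The distinction matters beyond the label. Section 8.1 says of a major bleed: "If patients meet criteria for a major bleed, they will have met a major safety endpoint and will be removed from the study"; Section 13.4 agrees. After a clinically relevant non-major bleed the patient need not leave the study (8.1, 13.6). Section 16.4 considers early termination of accrual on major bleeding rates alone. Section 16.21 promises a separate description, among bleeds more than 7 days after treatment discontinuation, only for major ones.

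**Working it through.** The plan states no figure for this point, so the check is an item-by-item comparison of the two definitions.

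| Criterion | Section 2.11, major | Appendix IV, Grade 3 |
|---|---|---|
| Hemoglobin fall ≥ 2 g/dL or ≥ 2 units transfused | yes | yes, same wording |
| 1. Intracranial | yes | yes |
| 2. Intraspinal | yes, joined with epidural | yes, epidural not named |
| 3. Intraocular | yes | yes |
| 4. Retroperitoneal | yes | yes |
| 5. Pericardial | yes | yes |
| 6. Intra-articular | yes | **no** |
| 7. Intramuscular with compartment syndrome | yes | **no** |
| 8. Fatal | yes | yes |

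Section 2.11 has 8 categories and Appendix IV has 6, so 8 − 6 = 2 are missing. Appendix IV has no category that 2.11 lacks, so it is strictly narrower. The note in 2.11 on what intracranial hemorrhage includes is also absent from the appendix, but it clarifies a category and does not add one.

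Take an overt intra-articular bleed with a hemoglobin fall below 2 g/dL and fewer than 2 units transfused.

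- Under 2.11 it is major because of its site.
- Under Appendix IV it is not Grade 3. It is Grade 2 if it led to a medical intervention, an unscheduled contact or a temporary stop of study treatment, and Grade 1 otherwise.

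Tracing that bleed through the plan:

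1. **Primary composite (2.11, 16.21).** At Grade 2 it still counts. At Grade 1 it would not, and Section 1.5 does not list minor bleeds among the events sent to adjudication. Grade 1 is unlikely for these bleed types, above all compartment syndrome, but the text allows it.
2. **Removal or continuation (8.1, 13.4, 13.6).** The two definitions lead to opposite dispositions. Under 13.4, data are entered only up to a major bleed, so classification also decides whether later events, including recurrent thrombosis, are observed.
3. **Monitoring (16.4).** The text does not say whether the major bleeding rates are site-graded or adjudicated. If site-graded, the mismatch carries through.
4. **Late bleeds (16.21).** A late bleed of an omitted type that is recorded as Grade 2 might not be described.

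The frequency of these events cannot be calculated. Section 16.1 gives 3.2% for major bleeding overall, and nothing in the documents divides it by site.

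**The case against.** The strongest reply is that the plan already contains the safeguards. Section 1.5 sends all major and clinically relevant non-major bleeds to a central, blinded, independent committee and bases the final analyses on its results. A site entry of Grade 2 therefore still reaches adjudication, and 2.11 names its own criteria as those for categorizing bleeds. The composite counts both categories. Most of this stands: it protects the primary comparison and, if the committee applies 2.11, the separate major-bleed summaries too. What it leaves open is that Section 1.5 does not name the committee's definition, and that adjudication may come after a site has already acted.

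Three stronger readings are tempting but not supported:

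- *Sites remove or keep patients according to the form's grade.* Sections 8.1 and 13.4 turn on meeting the criteria for a major bleed and mention neither Grade 3 nor Appendix IV. Restart under 8.1 also depends on the attending physician's judgment, although 13.6 is worded more firmly. The form itself is not in the documents; that it carries the Appendix IV text is an inference from its title and from Section 4.0.
- *The mismatch drives early termination.* Section 16.4 plans no formal interim analysis and sets no numerical boundary for major bleeding.
- *Three categories are missing.* Epidural can be read as part of intraspinal. Counting it separately gives three of nine; the clear count is two of eight.

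**Conclusion.** The point holds as an internal inconsistency with limited reach. Appendix IV is narrower than 2.11 by two of eight categories, and the documents do not say which text prevails. The primary comparison is largely protected; site classification, and what depends on it, is not fully protected.

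The size of the effect is unknown. A reader might infer it from the expected number of major bleeds: 0.032 × 185 = 5.9 per arm, so one reclassified event is 1/5.9 = 17% of that arm's count (0.032 × 176 = 5.6 and 18% without the 5% inflation). That is not an estimate of this defect. Any single reclassified event would have the same effect, and applying 3.2% to both arms ignores the design assumption that combined bleeding is halved on the lower dose (9% against 18%).

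The conclusion assumes that sites use Appendix IV as Section 4.0 directs. The consequence for the primary count further assumes that the committee applies 2.11. The mismatch is worth correcting before data are classified, and it does not call the primary analysis into question.

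**What to change.** Reconcile the two texts. Make the Grade 3 wording in Appendix IV, and any case report form or help text based on it, identical to the major bleeding definition in 2.11. Add a sentence stating that 2.11 governs wherever the protocol refers to major bleeding, including adjudication and the data used under 16.4. Section 2.11 is the natural reference because the protocol itself names its criteria for categorizing bleeds.

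The cost is one sentence in the appendix, one on precedence, and an update of any matching form text. If bleeds have already been graded, the Grade 1 and Grade 2 entries should be checked for the omitted types. Sample size, power and the primary test do not change, and no change to any stopping or restart rule is proposed.

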Appendix V
Phone Contact Sheet
Telephone Script

Protocol Title: A Phase III, Controlled, Randomized, Double-Blind Study Evaluating the Safety of Two Doses of Apixaban for Secondary Prevention of Cancer Related Venous Thrombosis in Subjects Who Have Completed at Least Six Months of Anticoagulation Therapy

IRB #:

Principal Investigator: [name]

“Good morning/afternoon. This is _____ calling from [name of institution].

May I speak to _____?”

(If participant is there proceed to the following:)

“I would like to ask you a few questions regarding your blood thinner medication, **apixaban** and the clinical trial in which you have been enrolled. This will allow us to gather very important information about the safety and benefit of using this medication in treating and preventing blood clots.”

“I would like to ask these questions related to our study after confirming your name”

Patient Name _____

1. Over the past month, have you missed any doses of your blood thinner medication?

____ Yes

If yes, approximately how many doses do you estimate that you have missed? _____

If yes, why was the dose missed? _____

____ No, I have not missed any doses of medication

2. Over the past month have you had another blood clot problem?

____ Yes, a DVT (must contact local medical doctor to obtain documentation)

____ Yes, a PE

____ Yes, both a DVT and a PE

____ Yes, something else (e.g. an arterial clot). Please describe: _____

____ No, I have not had any more clots.

3. While you have been taking this medication as recommended have you experienced any major bleeding which required hospitalization or blood transfusion?

____ Yes. Please describe _____

____ No

Any bleeding other than that from an injury? (For example a spontaneous bloody nose.)

____ Yes, Please describe _____

____ No

4. Over the past month, have you undergone any surgeries or invasive procedures?

Yes

If yes, what type of surgery/procedure did you have? _____

What was the date of the procedure? ____-____-____ (MM-DD-YY)

No, I have not had any surgeries or procedures

5. Which of the following best applies to your current activity rating: _____

- A. Fully active, able to carry on all activities before your disease without restriction
- B. Restricted in physically strenuous activity but ambulatory and able to carry out work of a light or sedentary nature, e.g., light house work, office work
- C. Ambulatory and capable of all self-care but unable to carry out any work activities. Up and about more than 50% of waking hours
- D. Capable of only limited self-care, confined to bed or chair more than 50% of waking hours
- E. Completely disabled. Cannot carry on any self-care. Totally confined to bed or chair

6. What is your current weight? _____

7. Have you started any new medications? List these _____

8. Have you had any new leg swelling?

Yes

i. If yes, suggest that the patient see their medical provider

No, I have not had any new leg swelling.

9. Have you had any new chest pain or shortness of breath?

Yes

i. If yes, instruct the patient to call 911/go to ER.

No, I have not had any new chest pain or shortness of breath.

Do you have any questions for me?

“Thank you for participating in our study.

NOTE: If there is any evidence of bleeding or clotting, review this with the attending clinician and obtain documentation from the local healthcare provider if patient gave consent.

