7.0 Protocol Treatment

7.1 Treatment Schedule

| Agent | Dose Level | Frequency | Route |
|----------|------------|--------------------------------------|-------|
| Apixaban | 2.5 mg | Twice daily for 12 months (365 days) | Oral |
| Apixaban | 5 mg | Twice for daily 12 months (365 days) | Oral |

*If a dose of apixaban is not taken at the scheduled time, the dose should be taken as soon as possible (+/-4 hours of the normal scheduled dose) on the same day and the prescribed dosing schedule should be resumed. If more than 4 hours late, then just wait for the next dose. The dose should not be doubled to make up for missed doses.

7.11 Scheduled visits every 30 days +/- 1 week (either in person or by scripted telephone interview with a study coordinator) should include a standardized assessment for recurrent thromboembolism, bleeding episodes, and adverse reactions. Patients should be instructed to report to the clinic immediately (or call 911/go to the Emergency Room) if they had any bleeding, or symptoms of recurrent deep-vein thrombosis, pulmonary embolism, or both. Written patient education materials will be provided to each patient outlining signs and symptoms to watch for regarding VTE recurrences (appendix VI). All suspected episodes of recurrent thrombosis should be investigated with the use of objective imaging.

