Appendix VII

Patient Compliance Information

1. Over the past month, have you missed any doses of your blood thinner medication?

Yes,

If yes, approximately how many doses do you estimate that you have missed?

If yes, why was the dose missed?

No, I have not missed any doses of medication

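### The phone script and compliance questions look back one month, but contacts may be up to 44 days apart, so up to about 14 days are not directly asked about

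*Combined protocol and SAP*

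**What the plan says.** **Timing of contacts.** The Test Schedule (4.0) sets them "Every 30 days after the start of treatment (± 1 week"), and section 7.11 repeats the interval and permits the telephone: "Scheduled visits every 30 days +/- 1 week (either in person or by scripted telephone interview with a study coordinator"). Where a return visit is not feasible, footnote 3 of the Test Schedule says that "a detailed history will be obtained by phone using a structured interview (see appendix V").

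**Look-back in the questions.** Three items in Appendix V are limited to one month: missed doses (question 1), clots (question 2: "Over the past month have you had another blood clot problem") and procedures (question 4: "Over the past month, have you undergone any surgeries or invasive procedures"). Appendix VII, which footnote 4 of the Test Schedule prescribes for compliance documentation, asks "Over the past month, have you missed any doses of your blood thinner medication". No item asks about the time since the last contact.

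**Items without that limit.** The major-bleeding item refers to time on the drug: "While you have been taking this medication as recommended have you experienced any major bleeding which required hospitalization or blood transfusion". The follow-up item on other bleeding and the items on new medications (7), leg swelling (8: "Have you had any new leg swelling") and chest pain or breathlessness (9) have no stated period.

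**What the answers feed.** Section 2.31 defines the secondary efficacy endpoint as recurrent VTE or arterial thromboembolism, the latter including MI, stroke and TIA. Section 8.2 requires the date and type of procedures and the reason for any temporary hold to be recorded.

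**The concern.** The look-back period and the contact window do not fit together. When two contacts are more than a month apart, a patient who answers questions 1, 2 and 4 literally reports nothing about the start of that interval. A shorter interval afterwards does not repair this, because its look-back falls on days already covered.

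What is at stake is ascertainment of the secondary recurrence endpoint in patients followed by telephone, together with the procedure record. For missed doses the limit reaches further, because Appendix VII applies to compliance documentation however the contact is made.

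A separate wording matter sits in the same question. Question 2 mentions arterial events only through an example, an arterial clot, under an open option. A patient who has had a TIA or a heart attack may not think of it as a clot.

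**Working it through.** The plan states no maximum interval between contacts, so there is no figure of its own to reproduce.

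**Inputs.** Interval 30 days and window ±7 days, anchored to the start of treatment (4.0, 7.11). Look-back of one month (Appendices V and VII), taken here as 30 days, with 28 and 31 as the range (assumption).

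**1. Longest compliant interval.** Interval = 30 + b − a, where a and b are the deviations of two consecutive contacts, each from −7 to +7.
- Maximum: 30 + 7 − (−7) = 44 days (for example day 23, then day 67).
- Minimum: 30 − 7 − 7 = 16 days.

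**2. Unasked days at the maximum.** 44 − 30 = 14 (44 − 31 = 13; 44 − 28 = 16). In the example, the call on day 67 looks back to day 37. If the next call is on day 83, it looks back to day 53. Days 23 to 37 are never directly asked about.

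**3. Other reading of the window.** If it were counted from the previous contact, the maximum interval would be 30 + 7 = 37 days, with 7 days unasked (6 to 9).

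**4. Average, if contact days are independent and uniform in the window (assumption).** Let D = b − a, which is triangular on −14 to +14.
- P(interval > 30) = 0.50.
- P(interval > 37) = 7² / (2 × 14²) = 49/392 = 0.125.
- Mean unasked days = E[max(D, 0)] = 14/6 = 2.33 per interval; 2.33/30 = 7.8%.
- Over the 11 intervals between 12 contacts: 11 × 2.33 = 25.7 of 330 days, again 7.8%.
- Counting whole days (15 × 15 pairs) gives 47% of intervals over 30 days and a mean of 2.5 unasked days (8.3%). With a 31-day month the mean is 2.0 days (6.7%); with 28 days it is 3.6 (12.1%).

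**5. Worse than average.** Twelve contacts alternating early and late give six 44-day intervals: 6 × 14 = 84 of 360 days (23%). A skipped contact, with its neighbours on time, gives a 60-day interval and 60 − 30 = 30 unasked days.

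**6. Scale in events (illustration).** Assume 12-month recurrence between 1.7% and 18%, spanning rates quoted in sections 1.4 and 1.1. With 185 per arm, that is 185 × 0.017 = 3.1 to 185 × 0.18 = 33.3 events. If every contact were by telephone and every event in unasked time were lost, 7.8% of these is about 0.2 to 2.6 events per arm.

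**The case against.** The strongest case against is that an unasked day is not a missed event. The negative answer options to questions 1, 2 and 4 carry no date, so a patient with a clot 38 days ago could not truthfully choose the one for question 2. Questions 8 and 9 have no look-back limit. Patients are told to report symptoms at once (7.11). Serious events go to the coordinating group whatever their attribution (10.4), and grade 3 and 4 events are collected whatever theirs (10.522). A Recurrent Thromboembolism form and a Dose Omissions form are due at each monthly evaluation (18.1), and a recurrence takes the patient off study (8.1, 13.5). Missed doses and procedures enter no analysis specified in section 16.

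Most of this stands, and it limits the size of the problem. It does not close the gap:
- The forms record what the contact brings out. For a patient seen only by telephone, that is largely the script.
- An undated answer under a dated question is ambiguous, and the patient may never hear the answer options.
- Questions 8 and 9 do not cover symptoms of upper-extremity, splanchnic or cerebral vein thrombosis, all of which qualify as index events under 3.12.
- Prompt reporting of symptoms does not capture missed doses or procedures.

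A reader might infer that about 8% of recurrences will be lost, or that 8% is a ceiling. The documents support neither. They give no share of telephone contacts and no distribution of contact days, and the figure is an average over an assumed distribution that other timing can exceed. Nor do they support extending the point to the primary endpoint, since the bleeding items have no one-month limit.

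**Conclusion.** The mismatch is real and minor. With windows anchored to the start of treatment, up to about 14 days between compliant contacts (13 to 16) are not directly asked about, and more after a skipped contact. The average of about 2.3 days per interval rests on uniform, independent contact days and a 30-day month. For clots and procedures it applies only to contacts made with the script.

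The number of events actually missed cannot be derived from the documents and is probably much smaller than the unasked time suggests. Any loss should be similar in the two blinded arms. It touches the secondary recurrence endpoint, procedure records and compliance data. The primary bleeding endpoint, its test and the sample size are unaffected.

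The arterial wording in question 2 is a separate, valid alignment with 2.31. Its effect on the specified analysis is limited, because section 16.23 analyses a DVT/PE composite.

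**What to change.** In Appendix V questions 1, 2 and 4, and in Appendix VII, replace the one-month phrase with *Since our last contact on [date]*, or *Since starting study drug* at the first contact. Unasked days then fall to zero for any interval, including after a skipped contact.

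Separately, add to question 2: *including a heart attack, stroke or mini-stroke (TIA)*.

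The cost is a few wording changes in two appendices, and the caller needs the date of the previous contact to hand. No visit, test, sample size or analysis changes.

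### The telephone script's catch-all bleeding question leaves out bleeding from an injury, which the primary endpoint counts; some under-counting is possible, probably small.

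*Combined protocol and SAP*

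**What the plan says.** **What is counted.** Section 2.11 gives this definition of clinically relevant non-major bleeding: "overt bleeding not meeting the criteria for major bleeding but associated with medical intervention, an unscheduled contact with a member of the health care team". A temporary stop of study treatment also qualifies. Appendix IV gives the same definition for its grade 2: "Clinically relevant non-major bleeding is defined as overt bleeding not meeting the criteria for major bleeding but associated with medical intervention". Neither place excludes a bleed because of its cause. The primary endpoint is "the proportion of patients who experience at least one such bleeding event within 12 months of beginning treatment", so the unit is the patient.

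**What is asked by telephone.** Question 3 of Appendix V has two parts. The first is "have you experienced any major bleeding which required hospitalization or blood transfusion". The second, the only catch-all, is "Any bleeding other than that from an injury? (For example a spontaneous bloody nose".

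**When the script is used.** Sections 3.19 and 7.11 allow the monthly assessment to be done in person or by telephone. Section 4.0, footnote 3, names the Appendix V interview as the substitute when a return visit is not feasible.

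**The concern.** The instrument and the endpoint do not cover the same events. Take a patient who falls, bleeds, and makes an unscheduled clinic contact without being admitted or transfused. That is a primary-endpoint event under 2.11, yet the patient can truthfully answer no to both parts of question 3. The adjudication committee described in 1.5 can classify only the bleeds that reach it.

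The gap falls mainly on clinically relevant non-major bleeding, the larger component of the composite. An injury bleed that is major only because hemoglobin fell by at least 2 g/dL, without admission or transfusion, is exposed in the same way. What is at stake is the completeness of the absolute bleeding rates, which are a main product of a safety trial.

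**Working it through.** **1. Can a qualifying injury bleed pass through the script?** Route by route, for a telephone month:

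| Injury bleed | Counted under 2.11? | Elicited by the script? |
|---|---|---|
| Led to admission or transfusion, and major | Yes | Yes, question 3, first part |
| Led to a temporary stop of study drug | Yes | Probably, through question 1 ("If yes, why was the dose missed") and Appendix VII ("Over the past month, have you missed any doses of your blood thinner medication") |
| Treated by a procedure | Yes | Possibly, through question 4 ("Over the past month, have you undergone any surgeries or invasive procedures") |
| Led to medical intervention or an unscheduled contact only | Yes | Not asked |

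The last row is the gap.

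**2. The plan's own figure.** Inputs from 16.1: 176 per arm, 9% vs 18%, two-sided 5%. For a pooled-variance Z test, power = Φ[(d − z·SE0)/SE1], with d = 0.09 and mean rate 0.135.
- SE0 = √(2 × 0.135 × 0.865/176) = 0.03643.
- SE1 = √((0.18 × 0.82 + 0.09 × 0.91)/176) = 0.03611.
- Two-sided (z = 1.960): Φ(0.515) = 69.7%, against about 70% stated.
- One-sided (z = 1.645): Φ(0.833) = 79.8%.

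Both are shown because 16.1 plans a two-sided test and 16.21 a one-sided one. That difference is a separate matter.

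**3. Exposed component.** From 16.1, non-major bleeding is 14.5 of 17.7 points: 14.5/17.7 = 81.9%. Expected endpoint patients: 176 × (0.09 + 0.18) = 47.5.

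**4. Assumed loss.** The documents give none of the shares needed, so these are assumptions. A missed bleed costs an endpoint patient only if no other qualifying bleed is recorded.

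Loss = 0.819 × (share of non-major bleeds due to injury) × (share in a phone-only month) × (share not reported another way) × (share with no missed dose) × (share that are the patient's only qualifying bleed).

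- Low: 0.819 × 0.05 × 0.25 × 0.25 × 0.50 × 0.80 = 0.10%, or 0.05 patient.
- Central: 0.819 × 0.15 × 0.50 × 0.50 × 0.667 × 0.85 = 1.74%, or 0.83 patient.
- Higher: 0.819 × 0.15 × 0.50 × 0.50 × 1 × 1 = 3.07%, or 1.46 patients. This keeps the central values of the first three shares, so it is not an upper bound.

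**5. Effect on power, under two patterns of loss.** In the proportional pattern both rates are multiplied by (1 − loss). In the equal pattern the same total is split evenly, so each arm loses loss × 0.27/2: 0.235 points in the central case and 0.415 in the higher case.

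| Case | Proportional: rates | Power, two-sided / one-sided | Equal: rates | Power, two-sided / one-sided |
|---|---|---|---|---|
| None | 9% vs 18% | 69.7% / 79.8% | 9% vs 18% | 69.7% / 79.8% |
| Low | 8.99% vs 17.98% | 69.6% / 79.7% | 8.99% vs 17.99% | 69.7% / 79.8% |
| Central | 8.84% vs 17.69% | 68.8% / 79.0% | 8.76% vs 17.76% | 70.3% / 80.3% |
| Higher | 8.72% vs 17.45% | 68.1% / 78.5% | 8.59% vs 17.59% | 70.8% / 80.7% |

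In the proportional pattern the difference shrinks. In the equal pattern it stays at 9 points while the variance falls. The documents do not say which pattern applies.

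**6. How far the assumption carries.** If 5% of all non-major bleeds were missed in proportion to each arm's rate, two-sided power would be 67.6%; at 10% it would be 65.4%, and at 20% it would be 60.8%. Shares that high would need most of the other reporting routes to fail.

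**The case against.** The strongest reply is that question 3 is not the only monthly inquiry about bleeding.
- The patient-contact row in 4.0 includes a bleeding assessment every 30 days and at end of treatment. It points to Appendix IV, which has no injury exclusion, as well as to Appendix V.
- The same schedule has a separate adverse event assessment at each contact.
- Section 18.1 requires a Non-CTCAE Bleeding Grading form and two adverse event forms monthly.
- Section 7.11 calls for a standardized bleeding assessment and tells patients to report any bleeding at once.
- The script's closing note sends any evidence of bleeding to the attending clinician.

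All of this stands, and it is why the effect is judged small. It does not close the gap. For a telephone contact the script is the named interview, self-report depends on the patient acting, the closing note operates only once a bleed is known, and the content of the 18.1 forms is not in the documents.

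A reader might infer that the trial loses power. The documents do not support that: it holds only if missed bleeds are proportional to each arm's rate, and the equal pattern raises power slightly. A reader might also infer a bias between doses. None is shown, since treatment is blinded and both arms use the same script.

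**Conclusion.** The mismatch in wording holds and can be confirmed by reading 2.11, Appendix IV and Appendix V together. Its consequence is some under-counting of the absolute bleeding rates. The size cannot be derived from the documents and is probably small: under the assumed shares, about 0.05 to 1.5 of 47.5 endpoint patients. The direction of any effect on power is unknown. In the central and higher cases it is about 0.9 to 1.6 points lower two-sided with proportional loss, or about 0.6 to 1.2 points higher with equal loss. These figures rest on five assumed shares and illustrate scale only. This is an inexpensive improvement to consider, not a threat to the comparison between arms.

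**What to change.** Make the script and the endpoint agree, in one of two ways.

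- If injury bleeds count, remove the exclusion from the second part of question 3, for example: *Have you had any other bleeding, including bleeding after an injury?* Follow a yes with the date, site, treatment, health-care contact and any study drug interruption, and leave classification to the adjudication committee.
- If injury bleeds are not meant to count, state that exclusion in 2.11 and Appendix IV.

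The first option costs one revised script page with IRB submission, about a minute per call, and some extra minor bleeds to grade. The second costs one added sentence in each of the two places, with IRB submission. Neither needs a new procedure or more staff.
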